#### Pregnancy testing

Medically supervised pregnancy tests with a minimum sensitivity of 50 mIU/mL must be performed for females of childbearing potential, including females of childbearing potential who commit to complete abstinence, as outlined below.

#### **Before starting lenalidomide:**

##### *Female Subjects:*

FCBP must have two negative pregnancy tests (sensitivity of at least 50 mIU/mL) prior to starting lenalidomide . The first pregnancy test must be performed within 10-14 days prior to the start of study drug and the second pregnancy test must be performed within 24 hours prior to the start of study drug. The patient may not receive study drug until the Investigator has verified that the results of these pregnancy tests are negative.

Male Subjects:

Must agree to practice complete abstinence or agree to use a condom during sexual contact with pregnant females or females of childbearing potential throughout the entire duration of lenalidomide treatment, during dose interruptions and for at least 28 days following lenalidomide discontinuation, even if he has undergone a successful vasectomy.

**During study participation and for 28 days following discontinuation from the study:**

Female Subjects:

- FCBP with regular or no menstrual cycles must agree to have pregnancy tests weekly for the first 28 days of lenalidomide treatment, including dose interruptions, and then every 28 days throughout the remaining duration of lenalidomide treatment, including dose interruptions, at lenalidomide discontinuation, and at Day 28 following lenalidomide discontinuation. If menstrual cycles are irregular, the pregnancy testing must occur weekly for the first 28 days of lenalidomide treatment, including dose interruptions, and then every 14 days throughout the remaining duration of lenalidomide treatment, including dose interruptions, at lenalidomide discontinuation, and at Day 14 and Day 28 following lenalidomide discontinuation.
- At each visit, the Investigator must confirm with the FCBP that she is continuing to use two reliable methods of birth control at each visit during the time that birth control is required.
- Counseling about pregnancy precautions and the potential risks of fetal exposure must be conducted at a minimum of every 28 days throughout the entire duration of lenalidomide treatment, including dose interruptions.

- If pregnancy or a positive pregnancy test does occur in a study patient, lenalidomide must be immediately discontinued.
- Pregnancy testing and counseling must be performed if a patient misses her period or if her pregnancy test or her menstrual bleeding is abnormal. Lenalidomide treatment must be temporarily discontinued during this evaluation.
- Females must agree to abstain from breastfeeding during study participation and for at least 28 days after lenalidomide discontinuation.

Male Subjects:

- Must practice complete abstinence or use a condom during sexual contact with pregnant females or females of childbearing potential throughout the entire duration of lenalidomide treatment, during dose interruptions and for at least 28 days following lenalidomide discontinuation, even if he has undergone a successful vasectomy.
- Counseling about the requirement for condom use during sexual contact with females of childbearing potential and the potential risks of fetal exposure must be conducted at a minimum of every 28 days throughout the entire duration of lenalidomide treatment, including dose interruptions.
- If pregnancy or a positive pregnancy test does occur in the partner of a male study patient during study participation, the investigator must be notified immediately.

Additional precautions

- Patients should be instructed never to give lenalidomide to another person and to return any unused capsules to the Investigator at the end of treatment.
- Female patients should not donate blood during therapy and for at least 28 days following discontinuation of lenalidomide.
- Male patients should not donate blood, semen or sperm during therapy or for at least 28 days following discontinuation of lenalidomide.
- Only enough lenalidomide for one cycle of therapy may be dispensed with each cycle of therapy.

**Appendix B – ECOG Performance Status Scale**

SCORE	DESCRIPTION
0	Fully active, able to carry on all pre-disease performance without restriction.
1	Restricted in physically strenuous activity but ambulatory and able to carry out work of a light or sedentary nature, e.g., light house work, office work.
2	Ambulatory and capable of all self-care but unable to carry out any work activities. Up and about more than 50% of waking hours.
3	Capable of only limited self-care, confined to bed or chair more than 50% of waking hours.
4	Completely disabled. Cannot carry on any self-care. Totally confined to bed or chair.
5	Dead.

**Appendix C – Response Evaluation Criteria****Disease Response Criteria****Response**

Complete Response (CR)

**Criteria for Response**

Requires all of the following:

- Disappearance of the original monoclonal protein from the blood and urine on at least two determinations for a minimum of six weeks by immunofixation studies
- < 5% plasma cells in the bone marrow on at least one determination
- No increase in the size or number of lytic bone lesions (development of a compression fracture does not exclude response)
- Disappearance of soft tissue plasmacytomas for at least six weeks.

Near CR

- Requires all of above except immunofixation remains positive
- Or normal FLC ratio

Partial Response (PR)

Requires all of the following:

- $\geq 50\%$  reduction in the level of serum monoclonal protein for at least two determinations six weeks apart
- If present, reduction in 24-hour urinary light chain excretion by either  $\geq 90\%$  or to < 200 mg for at least two determinations six weeks apart
- $\geq 50\%$  reduction in the size of soft tissue plasmacytomas (by clinical or radiographic examination) for at least six weeks
- No increase in size or number of lytic bone lesions (development of compression fracture does not exclude response)
- If the serum and urine M-protein are unmeasurable a  $\geq 50\%$  decrease in the difference between involved and uninvolved FLC levels is required in place of the M-protein criteria

Minimal Response (MR)

Requires all of the following:

- $\geq 25\%$  to  $\leq 49\%$  reduction in the level of serum monoclonal protein for at least two determinations six weeks apart
- If present, a 50 to 89% reduction in 24 hour light chain excretion, which still exceeds 200 mg/24hr, for at least two determinations six weeks apart.
- For patients with non-secretory myeloma only, a 25 to 49% reduction in plasma cells in the bone marrow for a minimum of six weeks
- no increase in size or number of lytic bone lesions (development of compression fracture does not exclude response)

Stable Disease

Not meeting the criteria for CR, PR or PD

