**Other: symptomatic hyperviscosity, amyloidosis, recurrent bacterial infections (> 2 episodes in 12 months)**

**5.2.1.1** Patients must have relapsed or refractory disease (refractory is defined as progression during treatment or within 60 days after the completion of treatment) requiring 2nd or 3rd line therapy (see Appendix C)

**5.2.1.2** Patients may have received lenalidomide and/or dexamethasone

**5.2.1.3** Patients with measurable disease defined as:

- Serum monoclonal protein > 0.5 g/dL and/or 0.2 g/24hr urine light chain excretion
- Patients with lower M-protein values or non-secretory myeloma will be eligible if measurable disease can be established, such as serum Freelite™ chain ratio > 5x normal limit, measurable soft tissue plasmacytoma > 2 cm by either physical exam and/or applicable radiographs (i.e. MRI, CT-scan) and/or bone marrow involvement > 30%

- 5.2.1.4** Age  $\geq 18$  years at the time of signing the informed consent form.
- 5.2.1.5** All necessary baseline studies for determining eligibility must be obtained within 14 days prior to enrollment. Serum pregnancy tests (sensitivity of at least 50 mIU/mL), for females of childbearing potential (WCBP) must be completed. The first test must be performed within 10-14 days, and the second test within 24 hours prior to initiation of lenalidomide.
- 5.2.1.6** Pre-study ECOG performance status 0-2. Patients with lower performance status based solely on bone pain will be eligible.
- 5.2.1.7** Patients must have adequate liver functions: AST and ALT  $\leq 3x$  upper limit of normal, alkaline phosphatase  $\leq 3.0x$  upper limit of normal, except if attributed to tumor, and bilirubin  $\leq 2 x$  upper limit of normal.
- 5.2.1.8** Patients must have amylase  $\leq 2.5x$  upper limit of normal
- 5.2.1.9** All study participants must be registered into the mandatory RevAssist® program, and be willing and able to comply with the requirements of RevAssist®.
- 5.2.1.10** Subject must be able to adhere to the study visit schedule and other protocol requirements
- 5.2.1.11** Subject must understand and voluntarily sign an informed consent document.

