**Secondary endpoints:** Although this study is not powered to compare response as well as duration of response to the 2 dose regimen, we will collect and analyze both using power analysis. Objective response rate is defined as the proportion of randomized subjects who have evidence of either partial response or complete response as determined using the EBMT and IMWG criteria. One-sided 95% confidence limits on the lower limit of the percentage of responders will be established to determine if this lower bound exceeds 45%. Duration of response is computed among the subgroup of subjects whose best response is PR or better. It is defined as is the time from when measurement criteria are first met for objective response until the date of progression or death. A subject with an objective response who does not have a progression event will be censored at the same time as he or she was censored under the primary definition of PFS.

The data on growth factors and other markers will be collected. For each protein, the proportion of patients who are up or down-regulated will be reported along with the 90% CI. The Fisher's exact test (two sided significance level of 5%) will be used to compare the proportions of patients with CR+PR for those who are upregulated vs. those who are down-regulated.

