**Criteria for Response**

Requires one or more of the following:

- > 25% increase in the level of serum monoclonal paraprotein, which must also be an absolute increase of at least 5G/dL and confirmed on a repeat investigation
- > 25% increase in 24-hour urinary light chain excretion, which must also be an absolute increase of at least 200 mg/24hours and confirmed on a repeat investigation
- > 25% increase in plasma cells in a bone marrow aspirate or on trephine biopsy, which must also be an absolute increase of at least 10%
- Only in patients without measurable serum and urine M-protein levels: the difference between involved and uninvolved FLC levels (absolute increase must be <10mg/L)
- Definite increase in the size of existing lytic bone lesions or soft tissue plasmacytomas or definite development of new bone lesions or soft tissue plasmacytomas
- Development of hypercalcemia (corrected serum calcium > 11.5 mg/dL or 2.8 mmol/L not attributable to any other cause)

Relapse from CR

Requires at least one of the following:

- Reappearance of serum or urinary paraprotein on immunofixation or routine electrophoresis confirmed by at least one follow-up and excluding oligoclonal immune reconstitution
- $\geq$  5% plasma cells in the bone marrow aspirate or biopsy
- Development of new lytic bone lesions or soft tissue plasmacytomas or definite increase in the size of residual bone lesions (not including compression fracture).
- Development of hypercalcemia (corrected serum calcium > 11.5 mg/dL or 2.8 mmol/L not attributable to any other cause).

**\*Note clarification to IMWG criteria for coding CR and VGPR in patients in whom the only measurable disease is by serum FLC levels:** CR in such patients a normal FLC ratio of 0.26-1.65 in addition to CR criteria listed above. VGPR in such patients is defined as a >90% decrease in the difference between involved and uninvolved free light chain FLC levels.

Based on the criteria for evaluating disease response and progression in patients with multiple myeloma treated by high-dose therapy and haemopoietic stem cell transplantation. Myeloma Subcommittee of the EBMT. European Group for Blood and Marrow Transplant. Br J Haematol. 102: 1998; 1115-1123. and International Myeloma Working Group. Criteria for the classification of monoclonal gammopathies, multiple myeloma and related disorders: a report of the International Myeloma Working Group. Br J Haematol 2003; 121: 749–757.

**10.1**      Time to Treatment Failure

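### Near CR as printed can be met by a normal FLC ratio alone, and the PR rules do not say how a patient with urine-only disease is to be coded

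*Combined protocol and SAP*

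**What the plan says.** **Near CR.** Appendix C gives near CR two bullets. The first asks for every CR item except negative immunofixation. The second reads, in full, "Or normal FLC ratio". The note at the end of the response table deals with patients whose only measurable disease is serum FLC and uses the ratio differently: "CR in such patients a normal FLC ratio of 0.26-1.65 in addition to CR criteria listed above".

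**Where response categories are used.** Section 10.3 defines ORR as the proportion with PR or CR and compares a one-sided 95% lower limit with 45%. On duration it says: "Duration of response is computed among the subgroup of subjects whose best response is PR or better". The duration item at the end of Appendix C starts the clock at CR or PR only.

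**Urine disease.** Section 5.2.1.3 defines measurable disease as "Serum monoclonal protein > 0.5 g/dL and/or 0.2 g/24hr urine light chain excretion", so urine alone is enough for entry. PR requires all its listed items. One is a 50% or greater "reduction in the level of serum monoclonal protein for at least two determinations six weeks apart". Another begins "If present, reduction in 24-hour urinary light chain excretion by either" and is met by a 90% fall "or to < 200 mg for at least two determinations six weeks apart". An FLC substitute is offered only when serum and urine M-protein are both unmeasurable. The MR urine item is: "If present, a 50 to 89% reduction in 24 hour light chain excretion, which still exceeds 200 mg/24hr".

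**The concern.** There are two separate weaknesses in the response definitions.

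First, a category placed above PR has a printed route that asks for no change from baseline. Someone coding from the text could place a patient with unchanged M-protein above a patient whose M-protein has halved.

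Second, the PR rule does not say what to do with its serum item when there is no measurable serum M-protein. The two available readings give opposite answers, and under the lenient one the PR cut-off in urine is the entry level itself.

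At stake are ORR, which carries the 45% bound, and duration of response. The trial is open-label, so leaving either choice to the time of coding means making it with treatment and outcome in view.

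**Working it through.** The plan gives no figure on this point. Its one related figure, 81.6% power for 50% against 20% dose reduction with 40 per arm (Section 10.5), is reproduced by the two-proportion normal approximation with pooled null variance (0.8155). It concerns the primary outcome and is untouched here.

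**1. Near CR by FLC ratio.** Section 5.2.1.3 asks for an abnormal FLC ratio only as one way for patients with low M-protein or non-secretory disease to qualify. A patient entering on serum M-protein above 0.5 g/dL may have a normal ratio. Read as a stand-alone route, the second near-CR bullet is then met at baseline. The same patient also fits Appendix C's stable disease, which excludes only CR, PR and PD.

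The consequence differs by analysis:
- ORR (Section 10.3): PR or CR; near CR not named.
- Duration subgroup (Section 10.3): PR or better; near CR enters if ranked above PR, as the appendix's order suggests.
- Duration start (Section 10.3): when objective response criteria are first met, so a patient with near CR only has no start date.
- Duration (Appendix C): CR or PR; near CR not named.

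**2. Urine-only patients and PR.** Entry level: 0.2 g = 200 mg/24 h. With baseline B in mg/24 h, the urine item of PR needs a fall greater than (B - 200)/B, or a 90% fall if that is smaller. The MR urine item needs a fall of at least 50% with more than 200 mg remaining, so 0.5 x B > 200, that is B > 400.

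| Baseline (mg/24 h) | Fall needed for PR urine item | MR urine item reachable? |
|---|---|---|
| 205 | >2.4% | no |
| 210 | >4.8% | no |
| 220 | >9.1% | no |
| 250 | >20% | no |
| 300 | >33.3% | no |
| 400 | >50% | no |
| 1000 | >80% | yes |
| 2000 or more | 90% | yes |

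The serum item decides whether this matters:
- *Applied literally:* a patient with no serum M-protein cannot show a 50% serum fall and never reaches PR. The FLC substitute does not help, because urine is measurable. Only CR remains open.
- *Waived:* the table applies, and below 400 mg PR asks for less than the 50% required in serum.

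**3. Chance readings, if the serum item is waived.** Assume a within-patient CV of 10-30% (not in the documents), independent log-normal readings and no true change. Two given readings both fall below 200 mg in 9.8-18.8% of patients at 210 mg, 0.02-5.0% at 250 mg and under 1% at 300 mg.

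**4. Sensitivity of the ORR bound.** The plan does not say whether the bound applies per arm. Exact (Clopper-Pearson) one-sided 95% lower limits with n = 40 are 40.9% for 22 responders, 43.3% for 23 and 45.8% for 24, so 24 are needed. With n = 80, 44 are needed (limit 45.2%). If the true rate is 45% and a fraction f of true non-responders is coded PR, the apparent rate is 0.45 + 0.55f:

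| f (assumed) | Bound passed, n = 40 | Bound passed, n = 80 |
|---|---|---|
| 0 | 4.1% | 4.6% |
| 2.5% | 5.8% | 7.6% |
| 5% | 8.2% | 11.8% |
| 10% | 14.8% | 24.4% |

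These values of f are illustrations. Only the urine limb can feed them, since near CR is not in ORR.

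**The case against.** **PR is not met by urine alone.** A reader might infer that any patient slipping from 205 to 199 mg becomes a responder. The documents do not support that. PR requires all its items, including the 50% serum fall and the plasmacytoma and bone-lesion items. A patient with measurable serum M-protein cannot reach PR through the urine cut-off. This stands, and it confines the second limb to urine-only disease.

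**Near CR is not in ORR.** A reader might also infer that patients coded near CR by a normal ratio push ORR over 45%. That is not supported either, because ORR counts PR and CR only. Near CR reaches an analysis through the words PR or better in Section 10.3.

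**The FLC bullet may mean less than it says.** It can be read as an alternative to the immunofixation item alone, leaving the marrow, bone and plasmacytoma items in force. That is a fair reading, but the text does not state it, and the FLC note shows a narrower use was available.

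**The urine cut-off is the adopted convention.** Section 7 commits to EBMT and IMWG criteria, and Section 3.2 describes an earlier trial in newly diagnosed patients with the same urine rule. This stands, and it argues against writing a 50% condition into PR itself. If the residual limit were also dropped from MR, every urine fall meeting MR from a 200-400 mg baseline would meet PR too, and such edits would change who leaves the study after cycle 4.

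**Noise and importance.** Two determinations six weeks apart limit single-reading error, and Section 10.3 says the study is not powered to compare response. Both are true. Neither settles how to code an unchanged patient with a normal ratio or a urine-only patient.

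**Conclusion.** The point holds in a limited form. As printed, near CR has an unconditional FLC route that some patients could satisfy at entry, and the plan's statements on duration disagree about whether near CR counts. For urine-only patients the serum item of PR is undefined: one reading bars them from PR, and the other lets a fall of a few percent from just above 200 mg qualify. From 200 to 400 mg the MR urine item cannot be met at all.

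The effect is confined to ORR and duration of response, both secondary. The primary outcome and its power are unaffected. The documents do not give the number of patients with urine-only disease near 200 mg or with a normal ratio at entry, so no count per arm can be claimed, and the pass probabilities above rest on assumed fractions. The direction of any bias in duration cannot be determined from the documents. The change is worth making because the gap is plain on the page and cheap to close before responses are coded.

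**What to change.** For coding ORR and duration of response:

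1. In Appendix C, replace the second near-CR bullet with: *and, where FLC is the only measurable disease, a normal FLC ratio*.
2. State that the serum item of PR does not apply when there is no measurable serum M-protein by the Section 5.2.1.3 definition.
3. State whether near CR counts in ORR and in duration, and make Section 10.3 and the Appendix C duration item agree.
4. Keep the adopted EBMT/IMWG urine cut-off. Add a sensitivity analysis of ORR and duration that counts urine-only responders only if urine light chain fell by at least 50%. By the arithmetic above, it can change the coding only for baselines below 400 mg.

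The sponsor should also reconcile the PR and MR urine items with the rule on staying on study after cycle 4, which depends on MR. No continuation rule is proposed here.

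The cost is a few lines of text and one extra analysis. The schedule already collects FLC and, for patients with urine protein, 24-hour urine, so no new tests are needed. ORR may come out slightly lower in the sensitivity analysis.

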**Response**

Progressive Disease

**Criteria for Response**

Requires one or more of the following:

- > 25% increase in the level of serum monoclonal paraprotein, which must also be an absolute increase of at least 5G/dL and confirmed on a repeat investigation
- > 25% increase in 24-hour urinary light chain excretion, which must also be an absolute increase of at least 200 mg/24hours and confirmed on a repeat investigation
- > 25% increase in plasma cells in a bone marrow aspirate or on trephine biopsy, which must also be an absolute increase of at least 10%
- Only in patients without measurable serum and urine M-protein levels: the difference between involved and uninvolved FLC levels (absolute increase must be <10mg/L)
- Definite increase in the size of existing lytic bone lesions or soft tissue plasmacytomas or definite development of new bone lesions or soft tissue plasmacytomas
- Development of hypercalcemia (corrected serum calcium > 11.5 mg/dL or 2.8 mmol/L not attributable to any other cause)

Relapse from CR

Requires at least one of the following:

- Reappearance of serum or urinary paraprotein on immunofixation or routine electrophoresis confirmed by at least one follow-up and excluding oligoclonal immune reconstitution
- $\geq$  5% plasma cells in the bone marrow aspirate or biopsy
- Development of new lytic bone lesions or soft tissue plasmacytomas or definite increase in the size of residual bone lesions (not including compression fracture).
- Development of hypercalcemia (corrected serum calcium > 11.5 mg/dL or 2.8 mmol/L not attributable to any other cause).

**\*Note clarification to IMWG criteria for coding CR and VGPR in patients in whom the only measurable disease is by serum FLC levels:** CR in such patients a normal FLC ratio of 0.26-1.65 in addition to CR criteria listed above. VGPR in such patients is defined as a >90% decrease in the difference between involved and uninvolved free light chain FLC levels.

Based on the criteria for evaluating disease response and progression in patients with multiple myeloma treated by high-dose therapy and haemopoietic stem cell transplantation. Myeloma Subcommittee of the EBMT. European Group for Blood and Marrow Transplant. Br J Haematol. 102: 1998; 1115-1123. and International Myeloma Working Group. Criteria for the classification of monoclonal gammopathies, multiple myeloma and related disorders: a report of the International Myeloma Working Group. Br J Haematol 2003; 121: 749–757.

**10.1**      Time to Treatment Failure

Time to treatment failure will be defined as the period of time, on study, from the first day of drug treatment to the time when progressive disease, treatment related toxicity resulting in discontinuation of treatment, or death (from any cause) is clearly documented.

**10.2**      Time to Disease Progression

Time to disease progression will be defined as the period of time, on study including follow-up, from the first day of drug treatment to the time when a disease progression or relapse is clearly documented

**10.3**      Duration of Response

Duration of response will be defined as the period of time, on study and including follow-up, from the first day of attainment of a response to treatment (CR or PR) to the time when a disease progression or relapse is clearly documented

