**Inclusion criteria**

**5.2.1.1 Subject was previously diagnosed with multiple myeloma based on standard diagnostic criteria as follows.**

**Diagnostic Criteria for Multiple Myeloma, Myeloma Variants, and Monoclonal Gammopathy of Unknown Significance****Monoclonal gammopathy of undetermined significance (MGUS)**

- M-protein in serum <30 g/l
- Bone marrow clonal plasma cells <10%
- No evidence of other B-cell proliferative disorders
- No myeloma related organ or tissue impairment (no end organ damage, including bone lesions)

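### Two progression criteria in Appendix C are wrong as written: the serum limb demands a rise of at least 5 g/dL, and the free light chain limb sets a ceiling where the serum, urine and marrow limbs set minimums

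*Combined protocol and SAP*

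**What the plan says.** Appendix C, under Progressive Disease, lists several limbs, any one of which is enough.

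- **Serum:** a rise in monoclonal protein of more than 25%, "which must also be an absolute increase of at least 5G/dL and confirmed on a repeat investigation".
- **Urine:** a rise in light chain excretion of more than 25%, "which must also be an absolute increase of at least 200 mg/24hours and confirmed on a repeat investigation".
- **Marrow:** a rise in plasma cells of more than 25%, "which must also be an absolute increase of at least 10"%.
- **FLC**, only where serum and urine M-protein cannot be measured: the involved-minus-uninvolved difference, with the condition "absolute increase must be <10mg/L". No percentage is given.
- **Lesions and calcium:** growing or new bone lesions or plasmacytomas, or hypercalcemia.

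None of the laboratory limbs says whether the rise is counted from baseline or from the lowest value reached.

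Section 5.2.1.3 sets the entry levels: "Serum monoclonal protein > 0.5 g/dL and/or 0.2 g/24hr urine light chain excretion". Patients below these levels may enter on an abnormal Freelite ratio, a plasmacytoma, "and/or bone marrow involvement > 30"%, or a combination.

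The definition is used in several places. Section 5.7 ends treatment on progression as Appendix C defines it. Section 7 names the EBMT and IMWG criteria and sends the reader to Appendix C for how to apply them. Sections 2 and 5.1 take patients with progressive disease after cycle 2 off study. Duration of response, a secondary endpoint, ends at progression or death in Section 10.3 and at progression or relapse in the Duration of Response item at the end of Appendix C.

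**The concern.** The serum increment is out of scale with the rest of the protocol. A patient can enter with an M-protein just above 0.5 g/dL, yet must gain 5 g/dL before the serum limb is met. The increment is also larger than the whole M-protein level that Section 5.2.1.1 uses to mark off MGUS ("M-protein in serum <30 g/l", that is 3 g/dL).

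The FLC condition points the wrong way. The other three laboratory limbs require a rise of at least some amount; this one requires a rise below some amount. It then excludes the large rises that ought to count.

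At stake are a stopping rule and the end date of a secondary endpoint. A patient whose only evidence of progression is serum M-protein could stay on a failing regimen until another rule applies. An FLC-only patient could be taken off for a trivial change, or not be called at all after a large one.

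**Working it through.** The plan reports no calculated figure on this point, so the check compares the printed thresholds with each other and with the entry levels.

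**1. Required rise divided by entry level** (Appendix C over Section 5.2.1.3)

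- Serum: 5 / 0.5 = 10
- Urine: 200 mg / 200 mg = 1
- Marrow: 10% / 30% = 0.33

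The serum ratio is 10 / 1 = 10 to 10 / 0.33 = 30 times the others. The factor of 10 applies at the entry floor; for a patient at 3.0 g/dL the required rise is 5 / 3 = 1.67 times the starting level. Against the MGUS level: 5 g/dL = 50 g/L, and 50 / 30 = 1.67.

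**2. Does the 25% condition do anything?** Both conditions must hold, so the level needed from a reference value x is max(1.25x, x + 5). The two terms are equal at x = 5 / 0.25 = 20 g/dL. Below that, only the 5 g/dL matters. From 3.0 to 6.0 g/dL the rise is 100% but only 3.0 g/dL, so the limb is not met.

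**3. How far off might the threshold be?** The documents do not give the right increment. I assume d = 0.17 g/dL (marrow ratio, 0.33 × 0.5), 0.5 g/dL (urine ratio, 1 × 0.5) or 1.0 g/dL (a generous upper value), with threshold max(1.25x, x + d). The illustrative patients halve their M-protein from 1.0, 2.0, 3.0 or 5.0 g/dL. As the reference is unstated, x may be either the baseline or the lowest value.

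| Reference x (g/dL) | Printed threshold | Threshold at d = 0.17 / 0.5 / 1.0 | Printed ÷ assumed |
|---|---|---|---|
| 0.5 (lowest, from 1.0) | 5.5 | 0.67 / 1.0 / 1.5 | 8.2 / 5.5 / 3.7 |
| 1.0 (baseline, or lowest from 2.0) | 6.0 | 1.25 / 1.5 / 2.0 | 4.8 / 4.0 / 3.0 |
| 1.5 (lowest, from 3.0) | 6.5 | 1.88 / 2.0 / 2.5 | 3.5 / 3.3 / 2.6 |
| 2.0 (baseline) | 7.0 | 2.5 / 2.5 / 3.0 | 2.8 / 2.8 / 2.3 |
| 2.5 (lowest, from 5.0) | 7.5 | 3.13 / 3.13 / 3.5 | 2.4 / 2.4 / 2.1 |
| 3.0 (baseline) | 8.0 | 3.75 / 3.75 / 4.0 | 2.1 / 2.1 / 2.0 |
| 5.0 (baseline) | 10.0 | 6.25 / 6.25 / 6.25 | 1.6 / 1.6 / 1.6 |

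The printed threshold is above the assumed one throughout, by a factor of about 1.6 to 8.2.

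**4. The gap for one responder.** A patient who falls from 3.0 to 1.5 g/dL reaches the 50% reduction for PR. Above 1.5 g/dL the value is no longer at that level, and Appendix C puts anyone who meets none of CR, PR and PD in stable disease. The serum limb is not met until 6.5 g/dL (from the lowest value) or 8.0 g/dL (from baseline).

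**5. FLC limb.** Illustration: the difference falls from 300 to 100 mg/L, a reduction of 200 / 300 = 67%, enough for the FLC form of PR. A rise of 9 mg/L (9 / 100 = 9%) satisfies the printed condition. A rise of 200 mg/L, back to the starting level, does not.

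**The case against.** The strongest reply is that the printed figures may never be applied. The protocol names the EBMT and IMWG criteria repeatedly, Appendix C says it is based on them, and few clinicians would read the FLC condition literally. This limits the practical effect but does not cure the text: Sections 5.7 and 7 both send the reader to Appendix C. If some sites follow the page and others the source, calls will differ between sites.

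Several limits stand in full. The urine, marrow, lesion and calcium limbs are intact. Relapse from CR has its own rule ("Reappearance of serum or urinary paraprotein on immunofixation or routine electrophoresis confirmed by at least one follow-up"). The cycle-4 rule removes patients without at least MR, which bounds exposure in non-responders. Both arms share the text, and Section 10.3 says the study is not powered for duration of response.

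Both faults turn on a character or two in text extracted from PDF, so the original page should be checked. A single misread character would not explain the missing FLC percentage or the missing reference value.

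A reader might infer more than the documents support:

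- **That 5 is a slip for 0.5.** Plausible, but the entry-level ratios differ among themselves (1 and 0.33) and an entry level serves a different purpose from a progression increment. They show that 5 is out of scale without fixing the right value.
- **That the threshold is too high by one fixed factor.** The factor depends on the patient, the reference value and the assumed minimum.
- **That responders will leave without a progression event and be censored.** The schedule requires a response assessment at discontinuation, Section 5.8 follows responders for survival, and the Appendix C definition of duration of response includes follow-up. What remains unclear about remaining on study, follow-up and censoring comes from other parts of the text and adds nothing here.

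**Conclusion.** Both limbs are wrong as written. This is a definition and threshold error, and it should be fixed. The fault in each limb rests on the protocol's own text. In patients whose only change is in serum M-protein or FLC, following the text can make progression late, missed or wrongly called, with effects on stopping treatment and on duration of response.

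The size is a range: about 1.6 to 8.2 times the threshold, under assumed minimums of 0.17 to 1.0 g/dL and illustrative patients. No delay in months and no number of FLC-only patients can be derived. Nor do the documents support a claim that the dose-reduction comparison or its power is undermined; that outcome is touched at most indirectly, through time on treatment.

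**What to change.** In Appendix C, Progressive Disease:

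1. Check the original page for the serum figure and the FLC inequality sign.
2. Replace the serum increment with a minimum on the scale of measurable disease. I assume 0.5 g/dL, to be confirmed against the cited EBMT/IMWG source.
3. Make the FLC limb a minimum increase. I assume more than 10 mg/L, with the figure, unit and required percentage confirmed from the same source.
4. State whether rises are counted from the lowest value or from baseline.

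Then notify sites and re-check progression calls and response end dates against the M-protein and FLC values already collected. The cost is two corrected lines, one added sentence, a site notice and a review of existing data. No new tests or patients are needed.
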